2.4.5 BASELINE DESCRIPTIVE STATISTICS

Baseline characteristics will be summarized by treatment arm. Continuous variables will be summarized by the mean and standard deviation. Categorical variables will be described by the proportion in each category (with the corresponding sample size numbers).

2.4.6 PLANNED INTERIM ANALYSES

9.4.6.1 INTERIM SAFETY ANALYSIS

Summary of safety data (AEs and SAEs) by treatment group will be presented to DMC at the planned interim analyses and at least every 6 months, or at other frequencies if requested by the DMC. AEs and SAEs will be coded using the Medical Dictionary for Regulatory Activities (MedDRA), counted both at the patient level and event level. Severity, frequency, and relationship of AEs and SAEs to study intervention will be presented by System Organ Class (SOC) and preferred term groupings. Safety monitoring will be ongoing (see **Section 8.3**). The unblinded statistical team will prepare these reports for review by the DMC.

9.4.6.2 INTERIM EFFICACY AND FUTILITY ANALYSIS

We plan to conduct two interim efficacy analyses of the primary efficacy endpoint at 33% and 67% of total information to allow early stopping of the study when there is sufficient evidence that the convalescent plasma group is superior. The p -family alpha spending function of $p=2.5$ with a one-sided significance level 0.025 will be used as a guide for the DMC (non-binding). The type I error spent at the interim efficacy analysis will depend on the actual information time of the interim analysis according to the alpha spending function. If the study is not stopped at interim, the remaining type I error will be spent at the final analysis of the primary outcome. For example, if the two interim analyses occur at exactly 33% and 67% information time, the efficacy boundaries in the z -scale are -2.947 and -2.401, respectively, and the cumulative type I error spent at the two looks are 0.002 and 0.009, respectively; the remaining type I error 0.041 will be allocated to the final analysis.

Conditional power will be presented as an additional guide to the DMC for futility stopping (non-binding). Conditional power is the probability of obtaining a statistically significant treatment

benefit of convalescent plasma at the end of the study given the data accumulated thus far and assuming a hypothesized treatment effect thereafter. If the conditional power is less than 10% under the original treatment effect assumption (30% vs. 20%), consideration should be given to stopping the trial.

Table 9 gives the operating characteristics of the early stopping boundaries for a study of 666 participants, assuming no missing data, the interim analyses are performed at 33% and 67% information time (222 and 444 participants, respectively), and true proportion of death or respiratory failure is 30% in the control group. When the plasma group also has 30% death or respiratory failure (that is, no difference between the two groups), the study has 5.2% probability of crossing the futility boundary at the first interim analysis and 59% probability of crossing the futility boundary at the second interim analysis. When the plasma group has a 10% absolute reduction as compared to the control group (that is, 30% vs. 20%), the study has 11% probability of crossing the efficacy boundary at the first interim analysis and 41% probability of crossing the efficacy boundary at the second interim analysis.

The unblinded statistical team will prepare these closed reports for DMC review and recommendations. Analyses will be presented with blinded codes for treatment arms to protect the possibility that the interim report may fall into the wrong hands. A DMC charter will further describe procedures and membership.

Table 9. Operating characteristics of the early stopping boundaries for a study with 666 participants, assuming the proportion of respiratory failure or death on or before day 28 is 30% in the control group and there are no missing data on the primary outcome. Each result is based on 100,000 simulations.

True absolute reduction	Probability of crossing boundaries at the first interim analysis at 33% information time (222 patients)		Probability of crossing boundaries at the second interim analysis at 67% information time (444 patients)	
	Crossing efficacy boundary	Crossing futility boundary	Crossing efficacy boundary	Crossing futility boundary
-10%	<0.001	0.477	<0.001	0.518
-5%	<0.001	0.202	<0.001	0.730
0%	0.002	0.052	0.007	0.591
5%	0.017	0.007	0.098	0.203
8%	0.056	0.001	0.266	0.060
9%	0.081	0.001	0.339	0.036
10%	0.112	<0.001	0.411	0.019
11%	0.149	<0.001	0.477	0.010
12%	0.201	<0.001	0.521	0.004

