2.2 SAMPLE SIZE DETERMINATION

Primary endpoint

The Chi-square test will be used to compare treatment arms on the proportion of death from any cause or respiratory failure up to and including Day 28, with two-sided significance level = 0.05.

A meta-analysis of studies of SARS coronavirus infection and severe influenza reported that convalescent plasma led to an absolute reduction in the risk of mortality from 7% to 23% and a 54% greater likelihood of discharge by day 22²⁵. These data suggest that the treatment benefit of convalescent plasma in reducing the risk of death and respiratory failure may be substantial, particularly early in hospitalization. For this trial we conservatively assume a 10% absolute reduction (30% in the control group and 20% in the convalescent plasma group) given that this trial allows local standard of care in both arms, which may include effective medications for COVID-19.

Table 6. Required number of participants to have 80%, 85% or 90% power for the primary outcome, assuming no missing data.

Proportion in the control group	Absolute reduction	Corresponding proportion in the plasma group	Number of participants needed		
			80% power	85% power	90% power
35%	11%	24%	532	610	712
	10%	25%	652	746	874
	9%	26%	858	976	1134
	8%	27%	1042	1192	1396
30%	11%	19%	474	542	634
	10%	20%	582	666	778
	9%	21%	730	834	976
	8%	22%	936	1072	1254
25%	11%	14%	400	458	536
	10%	15%	496	566	662
	9%	16%	624	714	836
	8%	17%	806	922	1080

Table 6 provides the total number of participants needed for 80%, 85% or 90% power to detect a range of differences in the primary outcome, using the z-test with a two-sided significance level = 0.05 and assuming no missing data. A total of 666 participants are needed to have 85% power for a 10% absolute reduction when the proportion of death or respiratory failure is 30% in the control group (**Table 6**). This sample size has 76% power to detect a 9% absolute reduction

when the control rate is 30% and has 90% (81%) power to detect a 10% absolute reduction when the control rate is 25% (35%) (**Table 7**).

Table 7. Power of a study of 666 participants to detect differences in the primary outcome, assuming no missing data.

Proportion in the control group	Absolute reduction	Corresponding proportion in the convalescent plasma group	Power
35%	11%	24%	88%
	10%	25%	81%
	9%	26%	72%
	8%	27%	61%
30%	11%	19%	91%
	10%	20%	85%
	9%	21%	76%
	8%	22%	66%
25%	11%	14%	95%
	10%	15%	90%
	9%	16%	83%
	8%	17%	72%

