We do not plan to inflate the target number of events for the planned interim analysis described in **Section 9.4.6** below. The planned early stopping boundaries are conservative and the impact on power is negligible: the power with 666 participants (with no missing data) is 84.0%.

Assuming 5% of participants have missing data on primary outcome (such as due to lost of follow-up or early withdrawal from the study), we plan to randomize **702** ($=702/0.95$) participants.

Key secondary endpoint

The key secondary endpoint is time to recovery up to and including Day 28. Currently there is limited information about the anticipated effect size or the proportion of participants who will recover by Day 28. A preliminary review of data from ACCT-1 demonstrated a recovery rate ratio of 1.312.

Table 8 gives the power of the study for time to recovery in a study of sample size 702, for a range of treatment to control recovery rate ratio and proportion of recovery by day 28. If approximately 70% of study participants recover by Day 28, a study of 702 participants will have 83% power to detect a recovery rate ratio of 1.3.

Table 8. Power for time to recovery for a study of 702 participants

Recovery rate ratio	Overall proportion of recovery by day 28			
	80%	75%	70%	65%
1.20	58%	55%	52%	49%
1.25	75%	73%	70%	66%
1.30	87%	85%	83%	80%
1.35	94%	93%	91%	89%
1.40	98%	97%	96%	95%

Number of sites and recruitment period

Based on CDW data, there were over 3000 Veterans admitted to VA Medical Centers for SARS-CoV-2 infections in January-April 2020, and 40-50% of them had respiratory failure or death within 28 days of hospital admission. In March-May 2020, the top 25 VA Medical Centers had on average 29 (median = 24) hospital admissions per month. Conservatively, assuming each participating site can randomize on average 2 participants per month, the target sample size 702 can be achieved by 15 months of recruitment at 25 sites. We estimate up to 2000 patients may be screened before enrollment and up to 1500 patients enrolled/consented in order to have 702 randomizations.

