2.4 STATISTICAL ANALYSES

2.4.1 GENERAL APPROACH

This is a double-blind controlled randomized trial testing a superiority hypothesis of convalescent plasma versus saline with a two-sided type I error rate of 5%. Secondary hypotheses have been ordered according to relative importance, with one key secondary hypothesis highlighted. These will be described according to the appropriate summary statistics (e.g., proportions for categorical data, means with 95% confidence intervals for continuous data, median for time-to-event data).

A statistical analysis plan will be developed prior to unblinding of study and database lock.

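### The 0.041 given as the type I error left for the final analysis subtracts a one-sided spend from a two-sided total; on the plan's own one-sided 0.025 scale 0.016 remains

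*Combined protocol and SAP*

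**What the plan says.** Section 9.4.6.2 plans two interim efficacy looks, at 33% and 67% information. A power-family spending function with p = 2.5 "with a one-sided significance level 0.025 will be used as a guide for the DMC". If the trial continues past both looks, "the remaining type I error will be spent at the final analysis of the primary outcome". A worked example for looks at exactly those times gives boundaries of −2.947 and −2.401, negative z favouring plasma. It adds that "the cumulative type I error spent at the two looks are 0.002 and 0.009, respectively", and ends: "the remaining type I error 0.041 will be allocated to the final analysis". No boundary is given for the final look.

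Elsewhere the error rate is two-sided. Section 9.2 (printed as 2.2) sets the Chi-square test of the primary endpoint "with two-sided significance level = 0.05", and Section 9.4.1 (printed as 2.4.1) describes a superiority trial "with a two-sided type I error rate of 5" percent. Section 9.2 also reports the effect of the interim looks on power: "the power with 666 participants (with no missing data) is 84.0" percent.

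**The concern.** The example moves from a one-sided scale to a two-sided one within a single sentence and does not say so. A remainder of 0.041 cannot come out of a budget of 0.025.

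The figure matters because it is the only number the plan attaches to the last decision threshold of the primary test. A reader who stays on the one-sided scale would put all of 0.041 into the benefit direction. A reader who thinks of the planned two-sided Chi-square test would split it evenly. Neither gives the one-sided 0.025 that the section sets. The conditional-power futility guide needs the same final critical value, and the section does not give it there either.

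**Working it through.** **Inputs.** From Section 9.4.6.2: spending α(t) = 0.025 × t^2.5, looks at 222 and 444 of 666 participants (t = 1/3, 2/3, 1). From Section 9.2: 30% vs 20%, 333 per arm, stated power 84.0%. From Sections 9.2 and 9.4.1: overall two-sided 0.05.

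**1. Reproduce the printed interim figures.**
- α(1/3) = 0.025 × (1/3)^2.5 = 0.0016, printed as 0.002.
- α(2/3) = 0.025 × (2/3)^2.5 = 0.0091, printed as 0.009.
- Solving for the boundaries by recursive integration with independent increments gives |z| = 2.947 and 2.401, which match to three decimals.

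With 0.05 in place of 0.025, the boundaries would be 2.726 and 2.131. The printed spend is therefore on the one-sided 0.025 scale.

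**2. Remainder.**
- One-sided scale: 0.025 − 0.009 = 0.016 (unrounded 0.0159).
- Symmetric two-sided scale: 0.05 − 2 × 0.009 = 0.032.
- Two-sided total minus one-sided spend: 0.05 − 0.009 = 0.041, the printed figure.

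**3. What each use of the figure implies at the final look**, after boundaries of 2.947 and 2.401:

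| Use at the final look | Final \|z\| for benefit | Overall benefit-direction error |
|---|---|---|
| 0.016 spent in the benefit direction (the spending rule) | 2.030 | 0.0250 |
| 0.041 spent in the benefit direction | 1.664 | 0.050 |
| 0.041 spent over a symmetric two-sided test | 1.991 | 0.0268 |
| 0.041 as a nominal one-sided level | 1.739 | 0.043 |
| 0.041 as a nominal two-sided level | 2.044 | 0.024 |

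The boundary 2.030 has nominal p = 0.021 one-sided, or 0.042 two-sided. If harm is tested only at the final look, at z = +1.960, the harm-direction error is 0.0250 and the two-sided total is 0.0500.

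**4. Which boundary the design used.** The drift at full information is 0.10 / √[(0.30 × 0.70 + 0.20 × 0.80)/333] = 0.10 / √(0.37/333) = 3.00.

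| Final boundary | Power by integration | Power by simulation (1,000,000 binomial trials, pooled z) | Stated |
|---|---|---|---|
| −2.030 | 84.1% | 84.0% | 84.0% |
| −1.664 | 91.1% | 91.0% | 84.0% |

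Integration with a pooled null variance and looks at 0.33 and 0.67 gives 83.7% at the rule's boundary, so the match does not depend on the approximation chosen.

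**5. Cross-check on Table 9.** At 30% vs 20%, the computed probabilities of crossing for efficacy at the two looks are 0.112 and 0.413. Table 9 prints 0.112 and 0.411, and the text gives a "41% probability of crossing the efficacy boundary at the second interim analysis". Spending from 0.05 would give 0.160 and 0.470. Second-look futility under the 10% conditional-power rule with a final value of 2.030 is 0.020 at a 10-point reduction and 0.205 at 5 points, against 0.019 and 0.203 printed. With 1.664 it would be 0.006 and 0.108. First-look futility under no effect fits less closely (about 0.04 against 0.052), but 1.664 gives under 0.01.

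**The case against.** The strongest reply is that 0.041 is correct on the trial's declared two-sided 0.05. Only the benefit direction is spent at the interim looks, so what is left is 0.016 for benefit plus an untouched 0.025 for harm, and 0.016 + 0.025 = 0.041. That sum is right, and it leads to z = −2.030 for benefit.

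It can be added that the figure sits in an example, that the governing rule (spend what remains) is correct and determines the boundary, that the power and Table 9 rule out −1.664, and that using 0.041 as a nominal two-sided level would be slightly conservative. An SAP and a DMC charter are also still to come.

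Most of this stands: the rule is sound, and nothing suggests that the design calculation was wrong. It does not rescue the sentence. The coherent reading needs an asymmetric final test, 0.016 on one side and 0.025 on the other, and no section describes one. The section names a one-sided budget of 0.025 and no harm-direction allocation. The test that is described, a two-sided Chi-square, would naturally split 0.041 evenly, and that gives a benefit-direction error of 0.0268. That further documents are due is a reason to settle the figure before it is copied into them.

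**Conclusion.** The concern holds. As written, the worked figure is wrong or at best mislabelled: on the scale used for the rest of the example the remainder is 0.016, not 0.041. Taken literally, 0.041 gives a one-sided error for benefit of 0.0268 (symmetric split) to 0.050 (all in the benefit direction), against 0.025 planned. The stated power and most of Table 9 agree with a final boundary of −2.030, so this is a fault in the written example and not an inflated design. It should be corrected because it bears on the final threshold of the primary test.

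The boundary values assume looks at exactly 1/3 and 2/3 information, the usual independent-increments normal approximation, and efficacy boundaries computed without credit for the non-binding futility guide.

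**What to change.** Replace the final clause of the example in Section 9.4.6.2 with wording such as: the remaining one-sided type I error of 0.016 is allocated to the final analysis in the benefit direction; the 0.025 in the harm direction is unspent at the interim looks, so the two-sided total is 0.05; with looks at exactly 1/3 and 2/3 information the final efficacy boundary is z = −2.030, to be recomputed from the actual information times. Add that conditional power uses the same final critical value.

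Carry the text into the SAP and the DMC charter when they are written. The cost is one clause and one added sentence. Sample size, interim boundaries, stated power and participant procedures are unaffected.

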9.4.6.3 ADMINISTRATIVE MONITORING

The DMC will also monitor study progress and conduct. This administrative monitoring will focus on participant intake (overall and within site), adequacy of randomization, adherence to study protocol (e.g., completeness of follow-up, study intervention adherence and withdrawals, study withdrawals, timely submission of data, timely resolution of data queries, randomization of non-

eligible patients), baseline comparability of treatment groups, and other operational aspects of the study.

2.4.7 SUB-GROUP ANALYSES

Subgroup analyses for the primary outcome will evaluate the treatment effect across the following subgroups:

- 1) Received study product (plasma/saline) ≤ 7 days vs. >7 days after onset of symptoms
- 2) Have ≤ 2 vs. ≥ 3 comorbidities at baseline (age ≥ 65 years, underlying chronic lung, heart, kidney disease, hypertension, diabetes, obesity or immunosuppression)
- 3) Age <65 vs. ≥ 65
- 4) BMI <35 vs. ≥ 35

A forest plot will display point estimates and confidence intervals across subgroups. Interaction tests will be conducted to determine whether the treatment effect varies by subgroup. We may adjust for selected baseline covariates in the assessment of interactions. We anticipate that convalescent plasma has a larger benefit in those treated early (≤ 7 days after onset of symptoms), having more comorbidities at baseline, or older (≥ 65 years old), and a smaller benefit in obese individuals.

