
4. To evaluate the safety of different investigational therapeutics as compared to the control arm as assessed by:
 
 • Cumulative incidence of SAEs through Day 29. • Cumulative incidence of Grade 3 and 4 clinical and/or laboratory AEs through Day 29. • Discontinuation or temporary suspension of study product administrations (for any reason) • Changes in complete blood count with differential, hemoglobin, platelets, creatinine, glucose, total bilirubin, alanine aminotransferase (ALT), aspartate aminotransferase (AST), and prothrombin time (PT) reported as international normalized ratio (INR) over time (analysis of lab values in addition to AEs noted above). 	
 • SAEs • Grade 3 and 4 AEs • Change in total WBC number, neutrophil number, lymphocyte number, hemoglobin, platelets, creatinine, glucose, total bilirubin, ALT, AST, and PT/INR from Day 1 to Days 2, 4, and 7 (while hospitalized); and Days 15 and 29 (if attends in-person visit or still hospitalized).
Exploratory	

1. To examine if the effect of convalescent plasma is associated with the days of symptoms at time of plasma administration
	
 • Plasma administered on day ≤ 7 vs. >7 days of symptoms on primary outcome

2. To examine if effect of convalescent plasma differs by comorbidities
	
 • Primary outcome in persons with ≤ 2 or ≥ 3 comorbidities (age ≥ 65 years, chronic lung, cardiac and renal disease, hypertension, diabetes, obesity and immunosuppression)

3. Research sample collection and management for future investigations:
 
Respiratory samples on days 1, 4, 7, 15, 29 and 30 mL of blood on days 1, 2, 4, 7 in hospital and days 15 and 29 in- or outpatient.
	
 • Sample Collection (Research lab draw with routine labs), preparation, labeling, shipping, storage and monitoring will be addressed in a future amendment.

4. Impact of donor convalescent plasma parameters on the activity of administered plasma
	
 • Donor plasma samples retained by Vitalant Blood services and provided to CURES-1 investigators will be tested for antibody levels, neutralization against SARS-CoV2, inflammatory and other mediators in relation to clinical and laboratory outcomes in study subjects.

World Health Organization (WHO) Ordinal Scale

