6.4 STUDY INTERVENTION COMPLIANCE

The study intervention consists of intravenous administration of 200-600mL of convalescent plasma or an equivalent volume of 0.9% saline administered in two equally divided doses, less than 12 hours apart. The order will be entered by the site LSI or authorized designee and study product will be administered by clinical staff according to standard procedures for transfusion of component blood products.

Compliance with study intervention will be assessed using case report forms entered by local site staff following completed transfusion of study intervention.

The reason for failure or partial administration of study product will be recorded by study staff.

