7.2 PARTICIPANT DISCONTINUATION/WITHDRAWAL FROM THE STUDY

Participants are free to withdraw from full participation in the study at any time upon request, without any consequences.

If a participant requests to be withdrawn from the study, the LSI or delegatee may offer the participant an option of limited participation. The two limited participation options that may be offered are:

1. A participant can choose to withdraw from receiving study product, but agree to all other follow-up, including study staff contact and laboratory testing.

OR

2. A participant may choose to withdraw from direct participation in all study activities but allow ongoing medical records review by study staff (no contact).

A participant may also choose to withdraw completely from all study activities. If a participant fully withdraws consent, no study procedures may be performed, and no more data may be collected as of the time point at which the patient withdrew consent.

In any of the situations above, study personnel will ascertain and clearly document in the EHR any limits to ongoing participation. A participant's usual medical care is not affected by whether study participation continues (fully or to a lesser degree) or ends.

If a participant withdraws consent or is withdrawn from the study by the Local Site Investigator (LSI), an Early Termination Form will be completed. Data collected up to the point of withdrawal will be used in the analyses. If a participant agrees to limited participation the site must complete a Reduced Participation form.

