8.2 BASELINE, RANDOMIZATION AND PRODUCT ADMINISTRATION

Baseline assessments should be performed before the first study product administration.

The following eligibility/baseline assessments can be done up to 72 hours prior to randomization time: demographic information (age, ethnicity, gender, body mass index), medical history/baseline comorbidities (e.g. obesity, smoking, diabetes, hypertension, cardiac, renal, liver, and lung disease), and physical exam.

Baseline clinical status data are collected right before randomization. Baseline vital signs (NEWS2) should be collected closest to randomization time and must be collected within 24 hours prior to randomization time.

The following additional baseline assessments are collected prior to study product administration:

- COVID-19 signs and symptoms, including day of onset,
- Medications for this current illness taken in the 7 days prior to Day 1 (See Section 6.5),
- Designated pre-admission medications by class (See Section 6.5),
- Adverse events (See Section 8.5),
- Safety and research labs (See Section 8.4).

Day 1 safety and research labs should be collected up to 24 hours prior to randomization and before first study product administration. Laboratory tests performed as part of routine clinical care within the same time period will be accepted for Day 1 safety laboratory tests.

Ideally, product administration should start on the same day as randomization (Day 1), but may be started up to 36 hours after randomization.

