8.3.5 EXPLORATORY ASSESSMENTS

• To evaluate the impact of onset of symptoms relative to the time of plasma on the effect of convalescent plasma on primary outcome	Plasma administered on day ≤ 7 vs. >7 days of symptoms on primary outcome

• To evaluate the impact of comorbidity on the effect of convalescent plasma on primary outcome	Primary outcome in persons with ≤ 2 or ≥ 3 comorbidities (age ≥ 65 years, chronic lung, cardiac and renal disease, hypertension, diabetes, obesity and immunosuppression)

• To evaluate the relationship of clinical, immunologic, inflammatory, metabolic, coagulation, endocrinologic and microbiologic outcomes.	Using stored nasal swab fluid, plasma and blood cells, we will test for antibodies, antibody activity, cytokines, RNA transcripts and soluble and cellular markers of COVID-19 perturbations.

• Characterize the impact of specific parameters of convalescent plasma administered to subject on immunologic, inflammatory, metabolic, coagulation, and endocrinologic outcomes in study subjects.	Using samples of administered convalescent plasma, determine specific antibody levels, neutralization, cytokines and other soluble markers in relation to these outcomes in the plasma of study subjects and their outcomes.

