2.3 POPULATIONS FOR ANALYSES

The primary analysis will be based on an intention-to-treat population, including all participants randomized. The safety analysis will be based on a modified intent-to-treat population consisting of all participants who received at least one dose of any study intervention.

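### The symptom-timing subgroup is defined by when product was received, so it is fixed after randomisation and has no category for randomised participants who are never infused

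*Combined protocol and SAP*

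**What the plan says.** The Sub-Group Analyses section lists four subgroups for the primary outcome. The first is "Received study product (plasma/saline) ≤ 7 days vs. >7 days after onset of symptoms"; the others are baseline comorbidity count, age and BMI. A forest plot and interaction tests are planned, and the section states an expected direction for timing: a larger benefit in those treated early.

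The same definition appears in two other places. Table 2 (section 3, first exploratory objective) gives "Plasma administered on day ≤ 7 vs. >7 days of symptoms on primary outcome". Section 8.3.5 gives the aim as "To evaluate the impact of onset of symptoms relative to the time of plasma on the effect of convalescent plasma on primary outcome".

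On timing, section 8.2 says product administration should ideally start on the day of randomisation but "may be started up to 36 hours after randomization". The same section lists, among assessments made before product is given, "COVID-19 signs and symptoms, including day of onset".

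On participants without product, section 6.4 says "The reason for failure or partial administration of study product will be recorded by study staff", and section 7.2 offers this form of limited participation: "A participant can choose to withdraw from receiving study product, but agree to all other follow-up".

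On the population, section 9.3 (printed as 2.3) says "The primary analysis will be based on an intention-to-treat population, including all participants randomized". A population defined by receiving a dose is named there for safety only.

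**The concern.** A subgroup comparison keeps the protection of randomisation only if membership is settled beforehand, or at least cannot depend on the assigned arm. Here it depends on a later event, receipt of product. Two gaps follow.

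- **Never infused.** These participants count in the primary analysis but have no timing value. Dropping them departs from all-randomised, and the loss may be related to outcome. The first exclusion criterion in section 5.2 covers only respiratory failure or death anticipated within 24 hours, while product may start as late as 36 hours. A participant could have a primary event before infusion and belong to neither category.
- **Arm-dependent membership.** If plasma were delivered later than saline, more plasma participants would cross from the early to the late category. This is an inference. The documents give no delay by arm.

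At stake is how far a statement about early treatment can be trusted. The primary test, the type I error and the sample size are not affected.

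**Working it through.** **1. When each subgroup is settled**

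| Subgroup | Based on | Settled |
|---|---|---|
| Symptom timing | Receipt of product | 0 to 36 h after randomisation (8.2) |
| Comorbidities | Count at baseline | Before randomisation (8.2) |
| Age | Also a randomisation stratum (6.3.1) | Before randomisation |
| BMI | Baseline demographics | Before randomisation (8.2) |

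Only the first depends on something that happens after randomisation.

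**2. How many could be unclassified**

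The documents give no rate of non-infusion. With assumed rates of 1%, 2%, 5% and 10% of the 702 to be randomised, about 7, 14, 35 and 70 participants would have no timing category.

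**3. Size of the possible bias**

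All inputs in this step are assumed:
- no treatment effect, 30% average risk, 351 per arm (702/2);
- symptom duration d at randomisation follows a gamma distribution with mean 6.5 and SD 3 days;
- risk = 0.30 + slope × (d − 6.5);
- infusion delay is uniform from 0 to twice its mean, capped at 36 h;
- a participant is early if d + delay ≤ 7 days.

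*Never infused, worked by hand (slope 0).* Suppose 5% of plasma and 2% of saline participants are never infused (18 and 7 of 351), and non-infusion is three times as likely in those with an event.
- Plasma: the rate without an event is 0.05/(0.7 + 3 × 0.3) = 0.03125, and with an event 0.09375. Risk among the infused = 0.30 × (1 − 0.09375)/0.95 = 28.62%.
- Saline: the rates are 0.0125 and 0.0375. Risk among the infused = 0.30 × (1 − 0.0375)/0.98 = 29.46%.
- Difference: about −0.85 points in each category.

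*All scenarios.* Shift in plasma minus saline, in percentage points, by numerical integration:

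| Mean delay, plasma vs saline | Never infused | Slope per day | Early | Late | Interaction |
|---|---|---|---|---|---|
| 6 vs 6 h | none | −0.03 | 0.00 | 0.00 | 0.00 |
| 12 vs 6 h | none | −0.03 | +0.34 | +0.63 | −0.29 |
| 18 vs 6 h | none | −0.03 | +0.68 | +1.28 | −0.59 |
| 18 vs 6 h | none | +0.03 | −0.68 | −1.29 | +0.61 |
| 18 vs 6 h | none | 0 | 0.00 | 0.00 | 0.00 |
| 6 vs 6 h | 2% vs 2% | 0 | 0.00 | 0.00 | 0.00 |
| 6 vs 6 h | 5% vs 2% | 0 | −0.85 | −0.85 | 0.00 |
| 18 vs 6 h | 5% vs 2% | −0.03 | −0.26 | +0.55 | −0.82 |
| 18 vs 6 h | 5% vs 2% | +0.03 | −1.39 | −2.23 | +0.84 |

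At 18 vs 6 h, 9.8% of plasma and 3.1% of saline participants cross the cut: 34 vs 11 of 351, an excess of 23.

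**4. Comparison with sampling error**

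Take the plan's 666 evaluable participants, split evenly over four cells (666/4 = 166.5), at the design risks of 30% and 20%.
- SE of the arm difference in one category = 100 × √(0.3 × 0.7/166.5 + 0.2 × 0.8/166.5) = 4.7 points.
- SE of the interaction = 4.71 × √2 = 6.7 points.
- The largest interaction shift is 0.84/6.7, about one eighth of a standard error.

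If the category is set by days from onset to randomisation, the shift is 0 in every scenario. That follows by construction, because neither delay nor non-infusion then enters the definition.

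**5. The three statements compared**

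The Sub-Group Analyses section covers both products and counts days after onset. Table 2 and 8.3.5 refer to plasma only, which read literally leaves saline participants unclassified, and they count by day of symptoms. The two units may be given up to 12 hours apart (6.1.2), and no section says which unit's time counts.

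**The case against.** The strongest case on the other side concerns weight. This is an exploratory objective. The interaction test is the plan's stated tool for judging whether the effect varies, and even the worst scenario moves it by about one eighth of a standard error. The figure of about 2 points needs unequal delay and unequal non-infusion together, with the slope sign that makes them add; with the opposite sign the shifts are −0.26 and +0.55. Unequal delay is not documented: units are held in the local blood bank (6.2.1), staff are blinded, and same-day start is the aim in both arms. With equal delay and no non-infusion the model gives zero. The objective as worded concerns timing at administration, so the plan's definition answers it directly. Participants without outcome data are already excluded from the primary analysis, so a forest-plot row can fall short of the all-randomised total for that reason too. Finally, section 9.4.1 (printed as 2.4.1) defers a statistical analysis plan that could settle the matter.

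Most of this stands as a limit on size. It does not remove the defect: the definition is post-randomisation, non-receipt is foreseen, and no rule for the never infused appears in the text. The forest-plot point reduces to an extra shortfall in this row compared with the other three. The objective as worded is a good reason to keep the infusion-time analysis, but as a supportive one.

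**Conclusion.** The concern holds. Timing is the only one of the four subgroups settled after randomisation, and it is undefined for randomised participants who are never infused. Both statements come directly from the text and need no assumption.

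The size does rest on assumptions: 0 to about 2 points of bias in a category's arm difference, and at most 0.8 points in the interaction. Those figures depend on assumed symptom durations, risk slopes, delays and non-infusion rates, none of which the documents give. Unequal delay by arm is a possibility, not a finding.

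The change should be made, though the trial's main conclusion does not depend on it. The reasons are that the plan states in advance which way this subgroup should go, and that the correction costs almost nothing.

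**What to change.** - In the Sub-Group Analyses section, Table 2 and section 8.3.5, define the subgroup as days from symptom onset to randomisation (≤7 vs >7), for all randomised participants in both arms.
- State one day-count convention and use it in all three places.
- Keep the time-to-infusion version as a supportive analysis. State how never-infused participants are handled and which unit's start time counts. The pending statistical analysis plan can carry these rules.

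The cost is wording only. Onset day is collected at baseline and randomisation time is already known; sample size and type I error do not change. There is one small downside: the new definition can differ from actual infusion timing by up to 36 hours, which the supportive analysis covers. A participant with an unknown onset day would still lack a category, but that gap cannot depend on the assigned arm.
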